#### **8.2 Statistical Analyses**

Volumetric, DT-MRI, neuropsychological, and functional outcome measures will be analyzed using general linear mixed models (GLMMs) to estimate differences across time points (pre- and post-treatment). We will examine all variables to determine that they are relatively symmetric and unimodal and examine residuals from each model to ensure reasonable adherence to model assumptions. The models will include time of assessment (pre- or post-treatment), and age (at study entry) as covariates and a random effect for subject to account for within subject correlation. Dependent variables will be the volume of whole brain gray matter, white matter, and CSF. Each dependent variable will be evaluated separately. Estimated differences at 6 months post treatment compared to pre-treatment will be reported along with 95% confidence intervals for all outcomes. We will also calculate probabilities of treatment benefit or clinically important effects.

##### *8.2.1 Volumetric Analysis and Neurocognitive Outcomes*

For volumetric analyses and neurocognitive outcomes, we will use the global test procedure recommended by Bagiella et al (Bagiella, 2010). This procedure allows analysis of multiple outcome measures in the assessment of intervention effects while controlling Type I error and maximizing power. To examine brain-behavior relations, we will first examine the distribution of variables to determine whether assumptions are met for Pearson or Spearman correlation approaches. To evaluate strength of brain-behavior relations, outcome scores will be correlated with specific macrostructural and microstructural metrics from the DTI. For global outcome, the GOS-EC score will be correlated with gray and white matter volumes and corpus callosum FA. For neurocognitive outcomes, the accompanying table shows the expected relations between outcomes and gray and white matter microstructural metrics. We expect positive correlation of dependent variables with FA and white and gray matter volume and negative correlation of dependent variables with MD.

Table 4:

Expected Relations of Neurocognitive Outcomes with Gray and White Matter Microstructure from Diffusion Tensor Imaging		
Neuropsychological Outcome	Microstructure: Gray Matter MD	Microstructure: White Matter FA
Processing Speed WAIS-IV Coding		Corpus callosum
Fine Motor 9-hole Pegboard Dexterity Test		Corticospinal
Verbal D-KEFS Verbal Fluency NIH Picture Vocabulary Test		Arcuate/superior longitudinal fasciculus
Working Memory NIH List Sorting Working Memory Test	Dorsolateral prefrontal cortex	
Declarative Memory Rey Auditory Verbal Learning Test	Lateral temporal cortex, hippocampus	
Attention NIH Flanker Inhibitory Control and Attention Test	Dorsolateral & ventrolateral prefrontal cortex	

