We propose to investigate changes (from enrollment to 6 months post infusion) in global measures of structural integrity in GM and WM using volumetric and DT-MRI based imaging according to the protocols described in the appendix/Investigator Brochure. T1-weighted images will be reviewed for image quality prior to performing morphometric analyses. Using Freesurfer v5.0.0 software (www.surfer.nmr.mgh.harvard.edu), each brain is skull-stripped and segmented into 3 classes of voxels: gray matter, white matter, and cerebrospinal fluid (Dale & Sereno, 1993; Dale et al., 1999). Subsequently, the cortex will be parcellated for individual gyri yielding morphometric measures of cortical thickness, volume, and surface area and measures of underlying white matter fractional anisotropy (FA) within each gyrus (Fischl & Dale, 2000).

Further, we will measure white and gray matter regions of interest and will correlate the degree of injury/preservation with functional and neuropsychological outcome measures. These measures have been validated in multiple studies and are recommended by a task force from NIH and NIDRR as common data elements for TBI outcome research (McCauley et al., in press) and for use in clinical trials in TBI (Bagiella, 2011). These measures were also selected to assess relations with specific white and gray matter structures that are particularly vulnerable to disruption by TBI. White matter: corpus callosum (processing speed), corticospinal tract (motor coordination). Gray matter: frontal lobe (fluency, attention, working memory) and temporal lobe (declarative memory).

1.3 Exploratory Objectives: Investigate if HB-adMSC infusion reduces the neuroinflammatory response to injury.

Microglial activation has been shown to occur after TBI and chronic activation is associated with WM loss over time. (Loane, 2014; Ramlackhansingh, 2011). We have confirmed these findings in a rodent model of TBI as well, using both the M1 microglial activation marker, IBA-1 as well as the TSPO ligand, PBR-28. [¹¹C]ER-176 is a Radioligand for the TSPO with adequate sensitivity to robustly image all three affinity genotypes in human brain (Ikawa, 2017). We plan to use the approach to image the neuroinflammatory response to injury. These imaging findings will be correlated with circulating inflammatory cytokines.

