## “A Clinical Trial to Determine the Safety and Efficacy of Hope Biosciences Autologous Mesenchymal Stem Cell Therapy for the Treatment of Traumatic Brain Injury and Hypoxic-Ischemic Encephalopathy”

### **8. STATISTICAL ANALYSIS PLAN**

#### **8.1 Sample Size and Power**

A total of 24 patients will be enrolled in the study. We do not provide a power analysis for any outcomes since no formal hypothesis testing will be conducted. Instead, we will calculate estimates of treatment effect and 95% confidence intervals for all measures. We will also calculate probabilities of treatment benefit using Bayesian analyses and conservative neutral priors. Given that this is a Phase 1/2a study, there are no prior studies from which we could derive informative priors. Therefore our approach will be to use neutral priors meaning that a priori they will be centered at a null treatment effect. However, we will restrict the prior range (ie, 95% prior credible interval) to exclude large treatment effects that are almost never observed in human clinical studies.

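### The brain-behavior correlations in 8.2.1 state no adjustment for head size (volumes) or age (volumes, FA, MD), and do not say which visit, or whether levels or changes, are used

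*SAP*

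**What the plan says.** SAP section 8.2.1, repeated in Protocol section 8.2.1, first looks at distributions to "determine whether assumptions are met for Pearson or Spearman correlation approaches". The global outcome "score will be correlated with gray and white matter volumes and corpus callosum FA". The text writes GOS-EC there; I read it as the GOS-E used elsewhere. Table 4 pairs the neurocognitive tests with regional MD or FA. On direction the plan says "We expect positive correlation of dependent variables with FA and white and gray matter volume", and it expects negative correlations with MD. It names no covariate, partial correlation or scaled volume, no visit, and no choice between levels and changes.

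SAP section 8.2 handles the same kinds of measure with mixed models that include time and "age (at study entry) as covariates". The volumes there are whole-brain gray matter, white matter and CSF. Protocol section 1.2 describes how each brain is "segmented into 3 classes of voxels: gray matter, white matter, and cerebrospinal fluid". Neither document mentions head size or intracranial volume.

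On size and purpose, SAP section 8.1 says "A total of 24 patients will be enrolled in the study" and "We do not provide a power analysis for any outcomes since no formal hypothesis testing will be conducted".

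**The concern.** Protocol section 1.2 wants to relate the extent of damage or sparing to function. Across people, an unscaled volume reflects head size as well as preserved tissue. Head size that has nothing to do with outcome acts as noise in the volume and shrinks the correlation.

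Age is a separate problem. Entry spans 18 to 55 years, and age can be related to both the imaging measure and the score. It can therefore create, inflate or mask a correlation with volume, FA or MD.

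The plan already treats age as relevant, but uses it where it does little. With complete pre/post pairs and a random subject effect, an additive age term leaves the within-subject difference unchanged. It is then not carried into the analysis that compares subjects with one another. At stake is whether the reported coefficients describe the relation that the protocol set out to estimate.

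**Working it through.** The plan gives no figure to reproduce: it states no correlation size, alpha or power for these analyses. Everything below is illustration.

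**Inputs from the documents:** n = 24 (SAP 8.1), so at most 24 pairs per correlation per visit; 95% intervals (SAP 8.1), taken as two-sided; age 18 to 55 (Protocol 3.1).

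**Assumptions, not in the documents:** a correlation of 0.5 between head-size-free volume and outcome; a share s of volume variance due to head size, from 0.2 to 0.8, with head size unrelated to outcome; age-volume correlation -0.2 to -0.6; age-outcome correlation +0.3 to -0.5.

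**1. Dilution by head size.** r_raw = r × sqrt(1 - s). The chance that the 95% interval lies above zero is Φ(atanh(r_raw) × sqrt(n - 3) - 1.96), with sqrt(21) = 4.583.

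- s = 0: r = 0.50; 0.549 × 4.583 - 1.96 = 0.56; chance 71%.
- s = 0.2: r = 0.45; 0.481 × 4.583 - 1.96 = 0.25; about 60%.
- s = 0.5: r = 0.35; 0.369 × 4.583 - 1.96 = -0.27; 39% to 40%.
- s = 0.8: r = 0.22; 0.228 × 4.583 - 1.96 = -0.92; 18%.

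A simulation starting from r = 0.40 with s = 0.6 gave 0.25 for raw volume and 0.40 once head size was removed, which agrees with the formula.

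**2. After adjusting for two covariates.** The standard error becomes 1/sqrt(n - 2 - 3) = 1/sqrt(19). If the partial correlation is 0.5: 0.549 × 4.359 - 1.96 = 0.43; chance about 67%.

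**3. Price of adjusting.** The smallest |r| whose interval excludes zero rises from tanh(1.96/sqrt(21)) = 0.40 to tanh(1.96/sqrt(19)) = 0.42. Break-even is where atanh(r_raw) × 4.583 = 0.549 × 4.359. This gives r_raw = 0.48 and s = 1 - (0.48/0.50)² ≈ 0.08. Under these assumptions the two degrees of freedom are repaid once head size explains more than about 8% of volume variance.

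**4. Age.** r_obs = r_partial × sqrt((1 - r_av²)(1 - r_ao²)) + r_av × r_ao, where r_av is the age-volume and r_ao the age-outcome correlation.

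- No true relation (r_partial = 0): (-0.2)(-0.1) = 0.02; (-0.4)(-0.3) = 0.12; (-0.6)(-0.5) = 0.30. If older subjects score better: (-0.2)(0.3) = -0.06 to (-0.6)(0.3) = -0.18.
- r_partial = 0.40 and r_av = -0.6: r_obs is 0.58 when r_ao = -0.5, but 0.13 when r_ao = +0.3.

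The sign of the age effect therefore depends on a quantity that the documents do not give. The same formula applies to FA and MD with their own age correlations.

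**5. Scale against sampling error.** At n = 24 an observed r of 0.40 has a 95% interval of about 0.00 to 0.69. The biases are moderate beside that, but not negligible.

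**The case against.** A reader might infer that the plan fixes raw, absolute volumes, compared between subjects, and that the correlations are therefore known to be both diluted and confounded. The documents do not go that far.

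- **Level or change is open.** Section 8.2.1 does not say, and Protocol section 1.2 opens the same objective with changes from enrollment to six months. If changes are correlated, head size largely cancels. The later sentence in 1.2 about relating damage or sparing to outcome favours levels but does not settle it.
- **A scaling step may exist elsewhere.** Protocol sections 1.2 and 5.1.1 refer to the Investigator Brochure for imaging detail, and it is not among these documents. What can be said is that the SAP states no adjustment. A step that changes the reported coefficient still belongs in the SAP.
- **The sizes are assumed.** No document supports a high head-size share. At 20% the gain from adjusting is only from about 60% to 67%. The age effect can run either way, so the net direction is unknown.
- **Test scores may already be age-standardised.** The documents do not say. If they are, and scores no longer vary with age, the spurious part disappears. Age would still remain in the imaging measures.
- **The yardstick is mine.** The plan disclaims hypothesis testing, so an interval excluding zero is not its criterion. GOS-E at entry takes only the values 3 to 6, so Fisher's z is a rough guide.
- **Reach is limited.** Table 4's pairs use FA and MD, so the head-size argument does not touch them.

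All of these limits stand. None of them supplies the missing specification.

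**Conclusion.** The point holds as a gap worth closing in a descriptive secondary analysis. Section 8.2.1 states no adjustment for head size or age, and leaves visit and level versus change open, while 8.2 adjusts the same measures for age. If levels are meant, unadjusted volumes do not isolate preserved tissue, and age is uncontrolled in the volume, FA and MD correlations.

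On the assumptions shown, head size takes a correlation of 0.5 to between 0.45 and 0.22. Age moves a null correlation by anything from -0.18 to +0.30. These are ranges over assumed inputs, not estimates for this trial.

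It would be too strong to conclude that the trial's correlations are biased by a known amount or in a known direction, or that its main results are affected. The primary safety objective and the pre/post estimates do not depend on this analysis.

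**What to change.** In section 8.2.1 of the SAP and the matching protocol section:

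- State the visit, and whether levels or changes are correlated.
- For level correlations, report partial Pearson or partial rank correlations with 95% intervals, adjusted for age at entry.
- For gray and white matter volumes only, adjust also for the gray + white + CSF total from the same segmentation, or for intracranial volume if the pipeline outputs it. The documents do not list intracranial volume as collected; the three components of the total are described.
- Show the unadjusted coefficients alongside.
- If the Investigator Brochure already scales volumes to head size, say so in 8.2.1 and drop the second covariate.

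The cost is SAP wording, slightly more analysis, and up to two degrees of freedom at n = 24 (one for FA and MD). At r = 0.5 the 95% interval widens from 0.12-0.75 to 0.10-0.76. No new data are needed if the segmentation total is used.

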5. OUTCOME EVALUATIONS

5.1 MRI Evaluations:

5.1.1 MRI Acquisition and Analysis:

IRB NUMBER: HSC-MS-19-0685
IRB APPROVAL DATE: 07/31/2023

The primary goal of acquiring whole brain MRI data is twofold: 1) to quantitatively assess macro- and micro-structural properties of GM and WM regions at two time points after injury using state-of-the-art neuroimaging acquisition/analysis methods 2) to investigate macro- and micro-structural correlates of behavior in terms of cognitive performance and underlying neuropathology in a hypothesis-driven manner. To accomplish these objectives, the MRI data needs to be collected using two different, yet complementary modalities of MRI: high-resolution anatomical MRI (aMRI) and diffusion tensor imaging (DTI). The following MRI acquisition sequences will be used:

Table 2: MRI Acquisition Sequences

	FOV [mm]	Matrix	Slice thickness	No of slices (TR [msec])	No of Directions	B0	TE [ms] (TI [ms])	Coil
DTI	240 (phase: A/P)	128x192x1 , 100 % phase (reconstructed to 256) ky_dir=2 ky_dir=0	3 mm	36-40 (13,000)	32	1000	80 (N/A)	8 Ch Head (asset)
3D FSPGR	240 (phase: L/R)	224x352x1 75%phase (reconstructed to 512)	1 mm	128 (9.5)	N/A	N/A	3.9 (450)	
B0 fieldmap FSPGR		256x256x2 (nex) Also, set rhccctrl to 3	1 mm	Same as Anatomical scans (50, angle 30 degrees, BW 16kHz)	N/A	N/A	10 ms and 15 ms	
BOLD	220 (phase: A/P)	64x64x1 (epiRT)	3mm	30 (cover whole head)	N/A	N/A	35	

The details of analysis of the imaging data go beyond the space limitations of the synopsis section but are described in more detail in the Investigator Brochure.

5.1.2 [¹¹C]ER-176 PET Imaging:

Upon meeting inclusion/exclusion criteria, subjects will be scheduled for a PET/DT-MRI scan. All female subjects will be given a urine pregnancy test prior to each PET scan. The results of this test will be kept as part of their confidential research record. A positive screen will disqualify them from participation in the study. Following their PET/DT-MRI scan, subjects will be contacted within 24-48 hours by a licensed study clinician to ascertain the presence/absence of unforeseen complications. Clinical complications will trigger an appropriate medical intervention and/or referral.

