8.2.1 Volumetric Analysis and Neurocognitive Outcomes

For volumetric analyses and neurocognitive outcomes, we will use the global test procedure recommended by Bagiella et al (Bagiella, 2010). This procedure allows analysis of multiple outcome measures in the assessment of intervention effects while controlling Type I error and maximizing power. To examine brain-behavior relations, we will first examine the distribution of variables to determine whether assumptions are met for Pearson or Spearman correlation approaches. To evaluate strength of brain-behavior relations, outcome scores will be correlated with specific macrostructural and microstructural metrics from the DTI. For global outcome, the GOS-EC score will be correlated with gray and white matter volumes and corpus callosum FA. For neurocognitive outcomes, the accompanying table shows the expected relations between outcomes and gray and white matter microstructural metrics. We expect positive correlation of dependent variables with FA and white and gray matter volume and negative correlation of dependent variables with MD.

Table 4:

Expected Relations of Neurocognitive Outcomes with Gray and White Matter Microstructure from Diffusion Tensor Imaging		
Neuropsychological Outcome	Microstructure: Gray Matter MD	Microstructure: White Matter FA
Processing Speed WAIS-IV Coding		Corpus callosum
Fine Motor 9-hole Pegboard Dexterity Test		Corticospinal
Verbal D-KEFS Verbal Fluency NIH Picture Vocabulary Test		Arcuate/superior longitudinal fasciculus
Working Memory NIH List Sorting Working Memory Test	Dorsolateral prefrontal cortex	
Declarative Memory Rey Auditory Verbal Learning Test	Lateral temporal cortex, hippocampus	
Attention NIH Flanker Inhibitory Control and Attention Test	Dorsolateral & ventrolateral prefrontal cortex	

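### The three planned gray matter MD–cognition correlations are unadjusted, so as specified they cannot separate microstructure from atrophy; add a regionally adjusted correlation beside each

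*SAP*

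**What the plan says.** Table 4 appears in section 8.2.1 of both documents under the title "Expected Relations of Neurocognitive Outcomes with Gray and White Matter Microstructure from Diffusion Tensor Imaging". Three domains sit in the column "Microstructure: Gray Matter MD":

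- working memory, with dorsolateral prefrontal cortex;
- declarative memory, with "Lateral temporal cortex, hippocampus";
- attention, with "Dorsolateral & ventrolateral prefrontal cortex".

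The other three (processing speed, fine motor, verbal) sit under "Microstructure: White Matter FA".

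On method, SAP 8.2.1 says "we will first examine the distribution of variables to determine whether assumptions are met for Pearson or Spearman correlation approaches". On direction it says "We expect positive correlation of dependent variables with FA and white and gray matter volume and negative correlation of dependent variables with MD". No covariate or partial correlation is named. The mixed models in SAP 8.2 adjust for time and age, but those models are separate from the correlations.

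For acquisition, the DTI row of Protocol Table 2 (section 5.1.1) gives a 240 mm field of view, a matrix of "128x192x1 , 100 % phase (reconstructed to 256") and 3 mm slices. Protocol 1.2 plans a FreeSurfer segmentation of the T1 images into gray matter, white matter and CSF, with thickness, volume and surface area for each gyrus. It does not link these outputs to MD. Protocol 1.2 and 5.1.1 both refer the reader to the Investigator Brochure for imaging detail.

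**The concern.** Free water diffuses much faster than water in tissue. A voxel holding part cortex and part CSF therefore returns a higher MD than the cortex alone. Where the cortex is thinner, or the hippocampus has shrunk beside a ventricle, the CSF share of the region rises and so does its measured MD, even if the remaining tissue is unchanged.

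Variable atrophy is plausible in this sample: a normal brain CT or MRI is an exclusion, and the injury must be more than 6 months old. If subjects with more atrophy also score worse, CSF share links MD to cognition in the direction the plan predicts. Finding the predicted sign would then not show a microstructural relation. SAP 8.2.1 treats macrostructural and microstructural metrics as distinct, yet part of the MD result could be the volume result seen a second time.

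A change in CSF share over 6 months could enter a pre-post gray matter MD estimate in the same way, and a single-arm study has no control group against which to judge it.

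**Working it through.** The plan states no voxel size, expected correlation or power for this analysis, so there is no figure of its own to reproduce.

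**1. Voxel size (Protocol Table 2).** Only one field-of-view figure is given, so a square field is assumed.
- 240/128 = 1.875 mm; 240/192 = 1.25 mm; slice 3 mm.
- Volume = 1.875 x 1.25 x 3 = 7.03 mm³.
- Reconstruction to 256 gives 240/256 = 0.94 mm in plane, but this is interpolation and adds no acquired resolution.

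**2. Effect of a CSF share on measured MD.** All inputs here are assumptions: tissue MD 0.8 and CSF MD 3.0 (x 10⁻³ mm²/s), CSF-to-gray-matter signal ratio k from 1 to 3 without diffusion weighting, and b = 1000 s/mm² (the 1000 stands in a column headed B0). With CSF fraction f:

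MD = −ln{ [f·k·e^(−3.0) + (1−f)·e^(−0.8)] / [f·k + 1 − f] }

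For f = 0.10 and k = 1: 0.1 x 0.0498 + 0.9 x 0.4493 = 0.4094, and −ln(0.4094) = 0.893, which is 11.6% above 0.8.

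| f | k = 1 | k = 2 | k = 3 |
|---|---|---|---|
| 0.05 | +5.7% | +11.1% | +16.2% |
| 0.10 | +11.6% | +22.0% | +31.4% |
| 0.20 | +24.5% | +43.9% | +60.0% |

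A rise of 5 percentage points in f, starting from 10% or 20%, raises MD by about 6% to 11% with no change in the tissue.

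**3. Induced correlation.** If CSF share is the only link, r(MD, cognition) = r(MD, f) x r(f, cognition). Taking 0.3 to 0.7 in size for each link (assumed), the result runs from −0.3 x 0.3 = −0.09 to −0.7 x 0.7 = −0.49.

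**4. What n = 24 can show.** The interval is tanh(atanh(r) ± 1.96/√21), and the two-sided 5% critical size of r is 0.404.

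| Induced r | 95% interval if observed | Chance of nominal significance |
|---|---|---|
| −0.09 | −0.48 to 0.33 | 7% |
| −0.25 | −0.59 to 0.17 | 22% |
| −0.49 | −0.75 to −0.11 | 71% |

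**5. Cost of adjusting for one covariate.** On the Fisher scale the standard error goes from 1/√(24−3) = 0.218 to 1/√(24−4) = 0.224, a ratio of √(21/20) = 1.025, or about 2.5% wider.

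**The case against.** The strongest objection is the Investigator Brochure. Removing CSF-contaminated voxels is the kind of pipeline detail that would be written there, and the Brochure was not supplied. A reader might infer from the silence of the two documents that MD will go uncorrected. That does not follow. What stands is narrower: the correlation method is set in the SAP, is not deferred, and contains no regional volume, thickness or CSF term.

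A reader might also take gray matter MD to be the plan's microstructure measure in general. It covers three of six domains. The other three use white matter FA, and the global outcome is paired with volumes and corpus callosum FA.

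On size, the induced correlation is the product of two assumed links, so it largely restates what was put in. It shows that the bias could matter, not how large it is here.

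The 6-month extension is only loosely anchored. SAP 8.2 covers DT-MRI measures in general, but the dependent variables it lists are whole-brain volumes, and no model of cortical MD change is named.

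A stricter remedy is also tempting: an eroded gray matter mask that keeps only voxels low in CSF at both visits. The acquisition argues against prescribing it. Removing one voxel from each side takes 2 x 1.25 = 2.5 mm to 2 x 3 = 6 mm, which could leave little cortex if cortex is 2 to 4 mm thick (assumed). A both-visits rule would also make baseline MD depend on the 6-month scan.

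Finally, this is a descriptive analysis in a 24-patient study whose primary objective is safety and which plans no formal testing of hypotheses. That limits the weight of the point but does not remove it.

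**Conclusion.** The point holds as a modest, inexpensive improvement. For the three gray matter MD pairings, an unadjusted correlation at this voxel size cannot tell a microstructural relation from differing atrophy, and the possible bias runs in the predicted direction. This rests on the square field of view read from Table 2 and on MD not already being freed of CSF by steps in the Brochure.

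The documents give no CSF fraction, diffusivity, signal ratio or link strength, so the 12% to 31% rise in MD at a 10% CSF share and the induced correlation of −0.09 to −0.49 are illustrations only. They do not support saying that the planned MD is a measure of atrophy or that the correlations will be spurious. The primary safety objective and the white matter FA pairings are outside this point.

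**What to change.** In section 8.2.1, for working memory, declarative memory and attention:

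- Report the unadjusted MD–outcome correlation and, beside it, a partial correlation adjusted for the same region's volume, cortical thickness or CSF fraction, each with a 95% confidence interval. Name the adjusting measure for each region before analysis. The gyral outputs in Protocol 1.2 do not name the hippocampus, so its measure needs stating.
- State that a negative MD correlation will be read as microstructural only if it persists after adjustment, judged on the estimate and interval because no formal test is planned.
- In any pre-post model of gray matter MD, add the same regional term as a sensitivity analysis.
- Cite whatever CSF masking the Investigator Brochure specifies, or say that there is none.

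The cost is SAP wording and a few extra estimates from a segmentation already planned. Intervals widen by about 2.5% on the Fisher scale for one covariate. Adjustment may also remove real injury signal that MD shares with atrophy, which is why both results should be shown.
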